8. CORRELATIVE/SPECIAL STUDIES

8.1 Archival tumor samples:

Histology, immunohistochemistry for lymphocyte subsets (include multi-marker studies such as MIB1 or other) and for Gene Expression profiling with additional analysis of immune subsets by Cibersort and for Gene Expression profiling within the immune cells by CibersortX. The latter dataset can be validated by performing LCM-SMART-3SEQ.

8.2 Tumor samples collected throughout study:

Histology, immunohistochemistry for lymphocyte subsets (include multi-marker studies such as MIB1 or other) and for gene expression profiling (GEP) with additional analysis of immune subsets by Cibersort and for GEP within the immune cells by CibersortX. The latter dataset can be validated by performing LCM-SMART-3SEQ.

8.3 Blood collection:

a) Determine ctDNA levels

- Draw blood into two Streck Cell-free DNA BCT tubes (10 mL each)
- Cell-free DNA will be extracted from plasma using QIAamp Circulating Nucleic Acid kit (Qiagen), according to the manufacturer's protocol. Germline DNA will be extracted from peripheral blood cells using DNeasy Blood & Tissue kit (Qiagen), following the manufacturer's protocol. Depending on the histological subtype of sarcoma, cell-free DNA will be analyzed for the presence of tumor-type specific point mutations and/or DNA copy number alterations. For the point mutation analysis, we will apply deep targeted sequencing by Cancer Personalized Profiling by deep Sequencing (CAPP-Seq). For detection of DNA copy number alterations, we will perform shallow whole genome sequencing. We have previously successfully applied both methods to profile tumor-derived genomic aberrations in cell-free DNA extracted from plasma of subjects diagnosed with leiomyosarcoma (Przybyl J, Chabon JJ, *et al.* Combination Approach for Detecting Different Types of Alterations in Circulating Tumor DNA in Leiomyosarcoma. *Clin Cancer Res.* 2018 Jun 1;24(11):2688-2699.)

b) Gene expression profiling on blood lymphocytes, followed by CibersortX to assess subsets. This data can then be compared to c)

- For gene expression profiling of blood cells, collect blood into two PAXgene Blood RNA tubes (2.5 mL each) manufactured by BD biosciences that are specifically optimized for RNA extraction from the blood cells.

c) Perform flow with purification of T-cells, followed by Gene Expression profiling

d) Perform proteomic analysis for cytokines

8.3.1 Blood Specimen Handling Instructions:

a) Prior to Collection:

- Using a permanent marker pen, record the required information (subject number) on the blood collection tube label.

b) Sample Collection and Handling:

- Draw blood into two Streck BCT tubes (10 mL each), and draw blood into two PAXgene Blood RNA tubes (2.5 mL each). Invert gently 10 times to mix.
- Blood drawn into PAXgene tubes should be frozen at -80C and sent directly to [name] lab on dry ice in batches of 40 tubes (so not each one separately).
- Blood drawn in the Streck BCT tubes should be sent to [name] laboratory of the Stanford University Medical Center for processing.

9. STUDY CALENDAR

	Pre-Study/ Baseline	Wk 1	Wk 4 (± 3 d)	Wk 7 (± 3 d)	Wk 10 (± 3 d)	Maintenance Every 4W± 1W	Off-study (post-30 dy ± 1 wk)	Follow-up ⁱ
Investigational Agents		X	X	X	X	X		
Cryoablation			X					
Informed Consent	X							
Demographics	X							
Medical History	X							
Concomitant medications	X	X	X	X	X	X	X	
Physical exam	X	X	X	X	X	X	X	
Vital signs	X	X	X	X	X	X	X	
Height	X							
Weight	X	X	X	X	X	X	X	
Performance status	X	X	X	X	X	X	X	
PRO-CTCAE Questionnaire ^a		X	X	X	X	X	X	
CBC with differential and platelets ^b	X	X	X	X	X	X	X	
Serum chemistry ^b	X	X	X	X	X	X	X	
EKG	X					(as clinically indicated)		
Adverse event evaluation ^c	X	X	X	X	X	X	X	
Tumor measurements ^d	X				X	X		
Radiologic evaluation (CT, MRI, X-ray) ^d	X				X	X ^d		
β-HCG ^e	X	X	X ^e	X	X	X ^e		
Other tests, as appropriate ^f	X		X					
Other correlative studies ^g		X	X	X	X		X	

- a. PRO-CTCAE Questionnaire will be completed by patients at each study visit before any assessments are performed. Questionnaires in English, Spanish, and traditional Chinese are attached in Appendix F.
- b. Metabolic comprehensive includes: albumin, alkaline phosphatase, ALT (SGPT), AST (SGOT), urea nitrogen, calcium, chloride, CO₂, creatinine, glucose, globulin, potassium, sodium, total bilirubin, total protein. These labs should be done at baseline within 14 days of first treatment, and within 72 hours of day 1 of each subsequent treatment.
- c. Adverse events are based on Common Terminology Criteria for Adverse Events (CTCAE) v5.0 Publish Date: 27 November 2017. Adverse events will be recorded from the time the subject signs informed consent through and including 30 days after the last dose of study drug. All serious adverse events will be tracked until resolution, or until 100 days after the last dose of study drug.
- d. Tumor measurements are based on RECIST v1.1 and irRECIST criteria (Appendices C & D). Scans will be done at baseline within 28 days of 1st treatment and then after dose 4 of immunotherapy (W 10 dose). This scan should be done at week 14 ± 1 week and every 12 weeks ± 1 week, once subjects start maintenance nivolumab. Ablated tumors will not be included as part of the treatment response assessment, ie, disease response; measurable disease; or tumor progression, by either RECIST or irRECIST. The baseline measurements will be done before treatment, and follow-up measurements will be done after 4 doses of ipilimumab and nivolumab (12 weeks), then every 12 weeks thereafter. At Investigator's discretion, imaging of known sites of disease is recommended.
- e. Serum β-HCG: Women of child-bearing potential are required to have a negative pregnancy test within 24 hours (eligibility criteria) prior to the initial administration of study drug, then every 3 to 4 weeks (± 1 week) during the study (this test can be omitted if subject is post-menopausal by either surgery or elevated FSH).
- f. ACTH, serum cortisol, TSH, free T4, CRP, ESR.
- g. Archival tumor sample must be available at baseline. All subsequent biopsies will be collected in paraffin for research purposes and standard diagnostics. Blood will be collected at baseline, and prior to treatment dose on weeks 1, 4, 7, 10 and during the off-study visit. Off study visit with a ± 1 week.
- h. Per protocol cryoablation is required to be performed before Week 4 administration of ipilimumab and nivolumab. (between Cycle 1 and Cycle 2), at the discretion of the investigator.
- i. Safety follow-up: After the off-study visit, there will be two additional follow-up phone call/or retrieval of medical records that occur every 35 days ± 1 week to collect information on participants' health status.

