3. PARTICIPANT SELECTION AND ENROLLMENT PROCEDURES

3.1 Inclusion Criteria

- 3.1.1 Unresectable or metastatic soft tissue sarcoma
- 3.1.2 ≥ 1 prior systemic therapy for sarcoma, including adjuvant systemic therapy
- 3.1.3 Age ≥ 18 years
- 3.1.4 Life expectancy > 3 months
- 3.1.5 Eastern Cooperative Oncology Group (ECOG) performance status 0 or 1
- 3.1.6 Lab values as below:
 - Absolute neutrophil count (ANC) $\geq 1,000/\text{mm}^3$
 - Platelet count $\geq 75,000/\text{mm}^3$
 - Creatinine $\leq 1.5 \times$ upper limit of normal (ULN) OR calculated (calc.) creatinine clearance $> 45 \text{ mL/min}$ using the lean body mass formula only
 - Total bilirubin $\leq 1.5 \times$ ULN in absence of Gilbert disease (total bilirubin $\leq 3 \times$ ULN with Gilbert); also, if hyperbilirubinemia is clearly attributed to liver metastases total bilirubin $\leq 3 \times$ ULN is permitted
 - AST/ALT $\leq 3 \times$ ULN
 - Thyroid stimulating hormone (TSH) within normal limits (WNL); supplementation is acceptable to achieve a TSH WNL; in subjects with abnormal TSH if free T4 is normal and subject is clinically euthyroid, subject is eligible
- 3.1.7 Any toxic effects of prior therapy (except alopecia) must be resolved to NCI CTCAE, version 5.0, Grade 1 or less
- 3.1.8 Ability to understand and the willingness to sign a written informed consent document
- 3.1.9 Women of childbearing potential (WOCBP) receiving nivolumab must be willing to adhere to contraception for a period of 5 months after the last dose of nivolumab. Men receiving nivolumab and who are sexually active with WOCBP will be instructed and must be willing to adhere to contraception for a period of 7 months after the last dose of nivolumab.

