4. TREATMENT PLAN

This is an open-label phase 2 study evaluating the safety and efficacy of ipilimumab/nivolumab in combination with cryotherapy.

The main primary objective of this study is to determine if immunotherapy in combination with cryoablation adds a clinically-significant benefit as measured by the objective response rate (ORR). The response rate will be evaluated by RECIST v1.1 as well as by irRECIST. Imaging by PET-CT or CT scan will be performed at screening, then every 12 weeks \pm 7 days until disease progression. Earlier scans will be performed if clinically indicated. Ablated tumors will not be included as part of the treatment response assessment, ie, disease response; measurable disease; or tumor progression, by either RECIST or irRECIST.

Subjects will receive ipilimumab 1 mg/kg IV over 30 minutes \pm 10 minutes and nivolumab 3 mg/kg IV over 30 minutes \pm 10 minutes every 3 weeks for 4 doses followed by nivolumab 480 mg IV over 30 minutes \pm 10 minutes every 4 weeks until progression or intolerance (maximum 24 months). The standard cycle of investigational agent treatment is considered to be 3 weeks. See Study Calendar at Section 9.

Per protocol cryotherapy (cryoablation) will be performed between investigational agent treatment Cycles 1 and 2 (see Section 5.3). Additional **cryoablation** procedures may be conducted as regular medical care per investigator discretion.

Blood samples will be drawn prior to each immunotherapy administration for routine tests as well as correlative studies. Blood and tissue samples will be retained and used for future research.

After completion of study treatment, a post-treatment biopsy will be obtained if feasible.

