6. DOSE MODIFICATIONS

There will be no dose modifications for the investigational agents.

Per-subject stopping rule

Subjects will be monitored for toxicity at every study visit during the treatment phase (through 10 weeks). As defined by the current US package inserts (USPIs) for nivolumab and ipilimumab, treatment will be withheld for the related adverse events (toxicities) specified therein, and additionally by the discretion of the investigator. Treatment may be resumed in accordance with the USPIs. In the event that toxicity is judged to be excessive, treatment will be terminated with one or both agents. Particular attention will be given to events that might be an overlapping toxicity.

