7. ADVERSE EVENTS AND REPORTING PROCEDURES

7.1 Potential Adverse Events

7.1.1 Ipilimumab (see appendix D for treatment algorithm)

Inflammatory Events (Immune-related Adverse Events or Immune-mediated Adverse Reactions)

Blockade of CTLA-4 by ipilimumab leads to T-cell activation, with the potential for clinical inflammatory AEs primarily involving the skin (dermatitis/pruritus), GI tract (diarrhea/colitis), liver (hepatitis), endocrine glands (eg, hypophysitis and adrenal or thyroid abnormalities), and other less frequent organs (eg, uveitis/episcleritis). The majority of these inflammatory AEs initially manifest during treatment; however, a minority occur weeks to months after discontinuation of ipilimumab. The majority of the inflammatory AEs are reversible with the guidance issued below.

- Gastrointestinal Toxicities

The most common site for ipilimumab-induced GI toxicity was the lower GI tract, and the most common presentation was mild to severe diarrhea or colitis with occasional bloody stools. In some cases, diarrhea began as mild and then worsened. Constipation was

rarely associated with ipilimumab administration. Delay in corticosteroid treatment may be associated with a poor outcome for subjects with high-grade diarrhea.

- Liver Toxicities

Subjects receiving ipilimumab may develop elevations in LFTs in the absence of clinical symptoms. Occasionally, subjects may present with symptoms, including right upper quadrant abdominal pain or unexplained vomiting. Most cases of inflammatory hepatitis responded to high-dose corticosteroids (IV route recommended).

- Endocrine Toxicities

The most common inflammatory endocrine toxicities are hypophysitis and hypopituitarism, secondary cortisol deficiency (hypoadrenalinism), hypothyroidism or thyroiditis. Symptoms of hypopituitarism and other endocrine toxicities were generally controlled with appropriate hormone replacement.

- Skin Toxicities

The most common inflammatory skin toxicities are rash and pruritus, mostly mild to moderate in severity. Two cases of fatal treatment-related toxic epidermal necrolysis have been reported in clinical trials.

- Neurological Toxicities

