7.1.2 Nivolumab (see appendix D for treatment algorithm)

- Pulmonary toxicities

Subjects can present with either asymptomatic radiographic changes (eg, focal ground glass opacities and patchy infiltrates) or with symptoms of dyspnea, cough, or fever. All subjects with Grade 3 to 4 pneumonitis should discontinue nivolumab and initiate treatment with high doses of corticosteroids.

- Gastrointestinal toxicities

Most cases present with diarrhea. However diverticular perforation should also be considered when subjects present with abdominal pain and fevers.

- Hepatic toxicities

Early recognition and treatment of elevated LFTs and drug-induces liver injury are critical to their management. The principal treatment for high-grade hepatic AEs is corticosteroids.

- Endocrinopathies

The events are typically identified through either routine periodic monitoring of specific laboratories (eg, TSH) or as part of a work-up for associated symptoms (eg, fatigue). Moderate- to high-grade cases were managed with hormone replacement therapy and, in some cases, with the addition of corticosteroids.

- Skin toxicities

The most common skin toxicities include rash and pruritus. Rashes are typically focal with a maculopapular appearance occurring on the trunk, back, or extremities. Topical corticosteroids can be used for some cases of rash. Anti-histamines can be used for some cases of pruritus.

- Renal toxicities

Elevated creatinine and biopsy-confirmed tubulointerstitial nephritis and allergic nephritis are seen infrequently.

- Neurologic toxicities

Neurologic AEs can manifest as central abnormalities (eg, aseptic meningitis, encephalopathy, or encephalitis) or peripheral sensory/motor neuropathies (eg, Guillain-Barre Syndrome, myasthenia gravis complicated with sepsis and fatality). The onset has been observed as early as after a single treatment with the nivolumab + ipilimumab combination.

- Infusion Reactions

Infusion reactions, including high-grade hypersensitivity reactions, following administration of nivolumab are uncommon. Investigators are advised to monitor for fever, chills, shakes, itching, rash, hypertension or hypotension, or difficulty in breathing during and immediately after administration of nivolumab. Study protocols provide explicit guidance on the management of infusion-related reactions.

- Lipase/Amylase Elevations

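### No TSH, free T4, cortisol or ACTH test is scheduled after week 4, the second of four combination doses: none later in induction, in nivolumab maintenance or at off-study

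*Combined protocol and SAP*

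**What the plan says.** The hormone tests appear in one row of the Study Calendar in section 9, labelled "Other tests, as appropriate". Note f gives the contents: "ACTH, serum cortisol, TSH, free T4, CRP, ESR". The row has a mark under Pre-Study/Baseline and under Wk 4. Its cells for Wk 1, Wk 7, Wk 10, Maintenance, Off-study and Follow-up are empty.

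Four other places bear on the point:

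- **Chemistry (note b).** This panel is drawn at baseline, at every dosing visit and at off-study. It is listed analyte by analyte, ending "creatinine, glucose, globulin, potassium, sodium, total bilirubin, total protein". No hormone is in the list.
- **Section 4.** "Blood samples will be drawn prior to each immunotherapy administration for routine tests as well as correlative studies". The routine tests are not named.
- **Section 6.** Under the current package inserts, "treatment will be withheld for the related adverse events (toxicities) specified therein". The reference covers withholding and resuming treatment.
- **Section 3.1.6.** TSH is an eligibility test. Supplemented subjects may enter, and "in subjects with abnormal TSH if free T4 is normal and subject is clinically euthyroid, subject is eligible".

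On how endocrine events come to light, section 7.1.2 says: "The events are typically identified through either routine periodic monitoring of specific laboratories (eg, TSH", and then gives the alternative route, a work-up prompted by symptoms such as fatigue. On timing, section 7.1.1 says of inflammatory events in general: "The majority of these inflammatory AEs initially manifest during treatment; however, a minority occur weeks to months after discontinuation of ipilimumab".

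**The concern.** Section 7.1.1 lists pituitary inflammation and failure, secondary cortisol deficiency and thyroid disease as the leading endocrine toxicities of ipilimumab. Section 7.1.2 offers two routes to detection, periodic laboratory tests and symptom work-up. After week 4 the calendar schedules only what supports the second.

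The week 4 sample also comes early. It can show little of the effect of the later combination doses and nothing of maintenance. Subjects admitted on thyroid replacement, or with an abnormal TSH and a normal free T4, have no scheduled recheck after that visit.

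What is at stake is patient safety: thyroid or adrenal failure that a scheduled test might have shown could be recognised later, once symptoms or an indirect change in sodium, potassium or glucose prompt a test. Section 7.1 describes these conditions as generally manageable with hormone replacement, so prompt detection can be acted on.

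**Working it through.** The plan states no figure to reproduce. The check is a reading of the calendar and some counting.

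**Step 1. Set the rows side by side.** The Follow-up cell is empty in every row below.

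| Row | Pre-Study | Wk 1 | Wk 4 | Wk 7 | Wk 10 | Maint. | Off-study |
|---|---|---|---|---|---|---|---|
| Study drug | – | X | X | X | X | X | – |
| Blood count, chemistry | X | X | X | X | X | X | X |
| Adverse events, examination | X | X | X | X | X | X | X |
| PRO-CTCAE | – | X | X | X | X | X | X |
| Note f tests (hormones) | X | – | X | – | – | – | – |

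The hormone row has as many cells as the header has columns (8), so nothing suggests a shifted column. After Wk 4, blood is scheduled in 4 columns (Wk 7, Wk 10, Maintenance, Off-study), and the hormone row is marked in 0 of these 4. The empty Wk 1 cell is not held against the plan, because the baseline test covers it.

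**Step 2. Place the last scheduled test in the dosing sequence.** Weeks from first dose = calendar week − 1. The combination doses therefore fall at 0, 3, 6 and 9 weeks, and the last scheduled hormone test at 3 weeks. If the Wk 4 sample is taken before that day's infusion, as section 4 says of pre-dose blood, it follows one dose only. Doses 2, 3 and 4 (3 of 4) are then given at or after the last scheduled test. The fourth dose comes 9 − 3 = 6 weeks after it. All maintenance doses also come later.

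**Step 3. Look for another source of the schedule.**

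- Note b: the itemised panel contains no hormone.
- Section 4: the tests drawn before each dose are not identified.
- Section 6: the package inserts are used for treatment decisions; no test schedule is named.
- Section 3.1.6 and the Appendix A checklist: TSH at eligibility only.
- Appendix D: the endocrine algorithm figure cannot be seen. The visible text around it concerns management of an event.

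None of these schedules a later hormone test.

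**Step 4. Count the panels that a fix would add.** Added panels = 2 (Wk 7, Wk 10) + maintenance visits tested + 1 (off-study). The documents do not fix the start of maintenance exactly, so it is assumed to be 12 or 13 weeks after the first dose.

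- Stops after dose 4: 2 + 0 + 1 = 3.
- Treated for 26 weeks: maintenance visits at 12, 16, 20, 24 or at 13, 17, 21, 25, which is 4 either way. Testing every second visit gives 2 + 2 + 1 = 5; testing every visit gives 2 + 4 + 1 = 7.

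**The case against.** The best defence is that symptom-triggered testing is a coherent choice. Section 7.1.2 gives symptom work-up as an alternative to periodic laboratories, and the plan does schedule what supports it: adverse event review, examination, vital signs, weight, performance status and PRO-CTCAE at every dosing visit and at off-study, with sodium, potassium and glucose in the chemistry panel. The row label leaves room for discretion. Section 7.1.1 adds that most inflammatory events are reversible under its guidance and that endocrine symptoms were generally controlled by replacement. All of this stands, and it limits the point to scheduled surveillance.

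The marks are also imperfect evidence of intent. Note g asks for correlative blood at baseline, yet that cell is empty; note d places a scan at week 14, while the mark stands under Wk 10. The unnamed routine tests in section 4 may in practice include TSH. This is a fair caution, but note f adds no visits, and for the EKG the calendar does write an as-needed entry under Maintenance. The hormone row has no entry there.

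A reader might infer three stronger things that the documents do not support:

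- *That endocrine safety goes unmonitored after week 4.* The continuing assessments above contradict this.
- *That related adverse events will be under-counted in Outcome 4.* That outcome is a descriptive count without a threshold, and nothing in the documents shows how many events, if any, would escape it.
- *That late onset is shown for endocrine events.* The sentence on onset after ipilimumab stops covers all inflammatory events, and no endocrine incidence is given.

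**Conclusion.** The point holds in a limited form. The calendar schedules TSH, free T4, cortisol and ACTH at baseline and week 4 only, so no hormone test is scheduled after the second of four combination doses, during maintenance of up to 24 months, or at off-study. This is more than a missing detail: a site that follows the calendar exactly would stop scheduled hormone testing there.

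In calendar terms the gap is 0 of the 4 later columns at which blood is already drawn. In clinical terms it cannot be sized, because the documents give no endocrine event rate and no basis for estimating how many events would be found late. The primary endpoint and the Simon two-stage rule are not affected.

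The conclusion assumes that the table was read correctly from the PDF and that neither the unseen Appendix D figure nor the undefined routine tests of section 4 sets a hormone schedule. If the sponsor did mean those routine tests to include TSH and cortisol, the calendar should say so, and the same edit does that. This is an inexpensive improvement in patient safety, not a flaw in the efficacy design.

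**What to change.** Amend the hormone row and note f of the Study Calendar as follows:

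1. Mark TSH, with free T4 if TSH is abnormal, and morning cortisol at Wk 7, Wk 10, at least every second maintenance visit, and off-study.
2. Add ACTH when cortisol is low.
3. Do not require or interpret cortisol while a subject is on systemic corticosteroids. Section 4.3 allows these on study and Appendix D makes them a primary treatment for immune-related events, and they confound the result.
4. Remove the discretionary qualifier for TSH and cortisol. It can stay for CRP and ESR.

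Blood is already drawn at each of these visits, so no visit is added. Cortisol needs a morning sample; before a dose, the 72-hour window for laboratory tests in note b gives some room to arrange it.

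The cost is about 3 extra panels for a subject who stops after dose 4 and about 5 for one treated for 26 weeks (7 if every maintenance visit is tested). Some incidental abnormal results will need work-up.
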